4.7.4.7 Further Investigation: Prentice, Williams and Peterson model

A Prentice, Williams and Peterson (PWP) model for total time will be fitted to further investigate any possible effect of correlation between events on the study results. If the correlated nature of the events is ignored, the CIs for the estimated rates could be artificially narrow ^[3]. Hence, in this further analysis, adjustments for within-individual correlation will be applied fitting the PWP model.

The model will include treatment group, pooled site, i.e. country, as detailed in [Section 4.9.1](#), and use of stable concomitant therapy with oral macrolides as covariates.

The data will be limited to a maximum number of recurrence events in order to avoid unreliable and unstable estimates. The maximum number of events considered in the model will be set up

CONFIDENTIAL

Sponsor:	Zambon S.p.A.	Protocol Number:	Z7224L01
----------	---------------	------------------	----------

to include the full set of events for at least 90% of the subjects, i.e. 90% of the subjects having at most this number of pulmonary exacerbations.

Hazard ratio and corresponding 95% CIs for treatment group will be presented.

4.7.4.8 Further Investigation: Non-Parametric ANCOVA Model on Ordered Score for Number of Pulmonary Exacerbations

An additional analysis will be carried out on a NCFB pulmonary exacerbation score applying a non-parametric analysis of covariance (ANCOVA) model with a randomisation-based methodology as proposed by Koch et al ^[4]. Considering the sample size foreseen for this analysis, there won't be any correction for type I error.

Subjects will be classified with a NCFB pulmonary exacerbation score of 0, 1 or 2, depending on their individual yearly rate of NCFB pulmonary exacerbations.

The individual yearly rate of NCFB pulmonary exacerbations will be calculated for each subject using the following formula:

- Individual yearly rate = number of NCFB pulmonary exacerbations / follow-up time (years).

The NCFB pulmonary exacerbation score will be:

- 0 if individual yearly rate = 0
- 1 if $0 < \text{individual yearly rate} \leq 1$
- 2 if individual yearly rate > 1

The model will include treatment group, pooled site, i.e. country, as detailed in [Section 4.9.1](#), and use of stable concomitant therapy with oral macrolides as covariates. No stratification variable will be included.

Treatment effect, i.e. the increase in the overall score for the active colistimethate sodium versus placebo, will be presented along with the standard error, associated test statistic and two-sided p-value. Additionally, the asymptotic 95% CI for the treatment estimate will be reported. Due to the fact that the p-value computation is based on the re-randomisation of the population, while CI is based on repeated random sampling theory there might be disagreement regarding the treatment effect using these two different approaches. Even if these occurrences are quite infrequent, it is worth stating that the p-value from the randomisation test is based on a more realistic and minimal assumption and should take precedence ^[5].

Individual yearly rate of NCFB pulmonary exacerbations and NCFB pulmonary exacerbation score will be presented in a listing. NCFB pulmonary exacerbation score will also be summarised presenting the number and percentages of subjects with a score of 0, 1 or 2.

4.7.5 Secondary Endpoints

A hierarchical testing procedure will be applied to the secondary endpoints of this study, as per the following order:

- CCI [REDACTED]
- [REDACTED]

CONFIDENTIAL

Sponsor:	Zambon S.p.A.	Protocol Number:	Z7224L01
----------	---------------	------------------	----------

- CCI [REDACTED]
- [REDACTED]
- [REDACTED]
- [REDACTED]
- [REDACTED]
- [REDACTED]
- [REDACTED]
- [REDACTED]

No test will be considered significant in this hierarchy unless every earlier test in it, including that for the primary outcome, is significant. For the purposes of this SAP, it is anticipated that only the time to first pulmonary exacerbation and CCI [REDACTED] total scores will be analysed for the PP Population in addition to the mITT Population.

4.7.6 Methods of Analysis for Secondary Endpoints

4.7.6.1 CCI [REDACTED]

The CCI [REDACTED] will be calculated as the time in days from the date of the first dose of IMP to the date at which the CCI [REDACTED].

- Time to CCI [REDACTED] = start date of CCI [REDACTED]. (It should be noted that this differs slightly from the CCI [REDACTED]. For time-to-event endpoints, generally the + 1 is not included because this overestimates the time by 1 day for every event.)

Subjects completing the trial without CCI [REDACTED] or who are discontinued prematurely CCI [REDACTED] will be considered as censored at the time of their last follow-up, i.e. at the date of treatment completion/discontinuation. For the analysis, the following formula will be applied:

- Censoring time (days) = (date of treatment completion/discontinuation - date of the first dose of IMP)

Kaplan-Meier estimates in each treatment group will be presented: median time to CCI [REDACTED], 25th and 75th percentiles and the corresponding CIs will be tabulated. The number of CCI [REDACTED] CCI [REDACTED] CCI [REDACTED] subjects at the beginning of the period, the cumulative number of subjects with CCI [REDACTED] at the end of the period and the estimated rates of pulmonary exacerbations at the end of the period with the associated 95% CIs will be presented by treatment group for the following study periods: (0-28] days, (28-90] days, (90-180] days, (180-270] days and (270 days - End of Treatment] as supportive statistics.

CONFIDENTIAL

Sponsor:	Zambon S.p.A.	Protocol Number:	Z7224L01
----------	---------------	------------------	----------

The estimate of the survivor function in each group will be displayed graphically using a Kaplan-Meier curve.

For the main analysis, a log-rank sum test will be used to compare the survival distributions of the two treatment groups. A two-sided p-value of <0.05 will be considered statistically significant.

A Cox proportional hazard regression model will be used to compare the treatment groups as supportive analysis. The model will include treatment group, pooled site, i.e. country, as detailed in Section 4.9.1, and use of stable concomitant therapy with oral macrolides as covariates.

The number of subjects considered in the model will be provided by treatment group. P-values of the effects based on the Wald chi-square test will be presented. Treatment effect (colistimethate sodium vs placebo) will be presented as the adjusted hazard ratio with the associated 95% Wald CIs. An adjusted hazard ratio <1 will indicate that colistimethate sodium increases the CCI compared to placebo.

To investigate the impact that discontinuations may have on the trial results, a CCI analysis will be conducted for the mITT Population. Discontinuers will be counted as failures with their last follow-up date, i.e. date of discontinuation, considered as the time of event.

The main analysis will also be repeated considering the subgroup of mITT subjects who were considered adherent, i.e. had an adherence until the first pulmonary exacerbation of at least 80%.

CCI Analysis for the Effect of Concomitant Antibiotic Therapy

A supportive analysis examining the impact of antibiotic use (by adding an additional covariate to the Cox proportional hazard regression model so that the hazard ratio is adjusted for this) will be conducted to determine if the use of antibiotics for conditions other than CCI has any impact on CCI.

The list of medications coded to WHO-DD Preferred Terms for antibiotics and anti-pseudomonal antibiotics are included in Appendix 3. If any medication in the list has a related CCI, the response to the question "CCI" on the CCI page for that CCI will then be checked to see whether or not the CCI in the opinion of the Investigator. If answered "No", the medication was not taken for a CCI and will be included as antibiotics used for conditions other than a CCI. Medications in the resulting list that do not have a related CCI will also be checked and included as antibiotics used for conditions other than a CCI.

Two additional tables will be presented:

- Supportive Cox proportional hazards analysis with use of any antibiotics for conditions other than a CCI (Yes/No) as an additional covariate.

CONFIDENTIAL

Sponsor:	Zambon S.p.A.	Protocol Number:	Z7224L01
----------	---------------	------------------	----------

- Supportive Cox proportional hazards analysis with use of any anti-pseudomonal antibiotics for conditions other than a protocol-defined pulmonary exacerbation (Yes/No) as an additional covariate.

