Summary statistics and analyses of the secondary efficacy/pharmaco-economic endpoints will be conducted for the mITT (main analysis) and the PP, as follows.

CCI
CCI
will be calculated as the time in days from the date of the first dose of IMP CCI
A log-rank sum test will be used to compare the treatment groups. Subjects completing the trial without CCI or who are discontinued prematurely CCI, will be considered as censored at the time of their last follow-up.

CCI
CCI will also be presented by treatment group. An appropriate non-parametric test will be used that makes allowing for the effect of prognostic covariates possible. This will be finalised in the SAP.

CCI

The number and the percentage of subjects CCI

CCI

The CCI total score and domain scores CCI will be summarised at each visit by treatment group using descriptive statistics. Changes from baseline (Visit 2) will also be summarised for each post-baseline visit by treatment group. Scores will be computed according to the CCI manual [20].

Multiple entries and missing data will be dealt with as described in the same manual.

CCI will be analysed using a linear mixed model for repeated measures including treatment, visit, treatment-by-visit interaction, use of stable concomitant therapy with oral macrolides and pooled sites as fixed effects and baseline value as covariate. An unstructured covariance matrix will be assumed and the Kenward-Roger adjustment will be used for the degrees of freedom. The least square means in each treatment group, the least square mean differences between treatments, their 95% CIs and associated p-values at each visit will be estimated by the model.

The CCI will be summarised and analysed similarly to the CCI CCI. Algorithm of scoring and methods for handling with multiple imputations and missing data will be performed according to the questionnaire instructions [21, 22].

CCI

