3.7 Randomisation

At Visit 2, eligible subjects will be randomised using the interactive web response system (IWRS) according to a pre-specified randomisation scheme such that they either receive colistimethate sodium or placebo. Site and use of stable concomitant therapy with oral macrolides (e.g. azithromycin or erythromycin or clarithromycin) (Yes/No) will be considered as factors for balancing randomisation, i.e. stratification factors. Thus, within each site, subjects with oral macrolides use will be randomised independently from subjects without use of macrolides, to receive colistimethate sodium or placebo in a 1:1 ratio. The randomisation within each site and nested level macrolide use will be done with blocks to guarantee a good balance between colistimethate sodium and placebo at any stage of the enrolment.

Note: according to Exclusion Criterion 15, the decision on whether stable concomitant antibiotic therapy with oral macrolides will be administered to a subject or not will have been taken at least 30 days prior to the Screening Visit (Visit 1). The treatment with oral macrolides should be continued throughout the trial in order not to jeopardize the study results.

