4.7.6.5 CCI

The time to first severe NCFB pulmonary exacerbation will be analysed and tested using a log-rank test as detailed in Section 4.7.6.1 for the CCI.

A log-rank sum test will be used to compare the survival distributions of the two treatment groups. A two-sided p-value of <0.05 will be considered statistically significant.

The above summary/analysis will be performed using the mITT Population.

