4.14 Algorithms/SAS Codes

The SAS codes for descriptive statistics and frequency counts detailed below are examples only and other procedures may be used, if appropriate.

- **Tables that need descriptive statistics – continuous variables:**

```
PROC UNIVARIATE DATA=dset NOPRINT;
  VAR var1 var2 var3 ...varn;
  BY byvar; (optional)
  OUTPUT OUT= outset
  N=n MEAN=mean MIN=min MAX=max MEDIAN=median STD=std *Q1=q1
  Q3=q3; *Include Q1 and Q3 for CCI data only;
RUN;
```

- **Tables that need frequency counts:**

```
PROC FREQ DATA=dset NOPRINT;
  BY byvar; (optional)
  TABLES var1*var2 /out= outset;
RUN;
```

- **Tables that need T-Test;**

```
PROC TTEST DATA=dset;
  CLASS var1;
  VAR var1N;
RUN;
```

- **Tables that need exact 95% CIs for risk difference between groups for proportions and Fisher's Exact:**

```
PROC FREQ DATA=dset;
  BY byvar; (optional)
  TABLES var*treatment / MEASURES RISKDIFF EXACT ALPHA=0.05;
  EXACT MEASURES;
  OUTPUT OUT= outset EXACT MEASURES RISKDIFF;
  WHERE wherever; (optional)
RUN;
```

- **Tables that need 95% CIs within group for binomial proportions:**

```
PROC FREQ DATA=dset;
  BY byvar; (optional)
  TABLES var1;
  EXACT BINOMIAL;
  OUTPUT OUT= outset BINOMIAL;
RUN;
```

- **Tables that require analysis of (co)variance and 95% CIs between arms for continuous variables:**

```
PROC GLM DATA= dset OUTSTAT=outset;
  CLASS treatment psite med;
```

CONFIDENTIAL

Sponsor:	Zambon S.p.A.	Protocol Number:	Z7224L01
----------	---------------	------------------	----------

*MODEL change = treatment psite med baseline/ SOLUTION;
LSMEANS treatment / STDERR PDIFF CL OBSMARGINS;
BY byvar; (optional)
WHERE wherever; (optional)*

RUN;

Notes:

- Psite represents the pooled site, i.e. country, as detailed in [Section 4.9.1](#);
- Med represents use of stable concomitant therapy with oral macrolides (e.g. azithromycin or erythromycin or clarithromycin) (Yes/No);
- Change represents the change from baseline of the variable;
- Baseline represents the baseline value of the variable;
- Treatment order: 1= Colistimethate Sodium, 2= Placebo.

- **Tables that require Kaplan-Meier estimates and log-rank test:**

*PROC LIFETEST DATA=dset OUTSURV=LIFE METHOD=KM timelist=(0 28 90 180
270 EoT) reduceout;
TIME time*event (1);
ID subject;
STRATA treatment;
WHERE wherever; (optional)
RUN;*

Notes:

- Time represents the time to event or time to censoring;
- Event represents the censoring indicator (1 = censored);

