The number of subjects considered in the model in each treatment group will be presented. The value of δ at which the conclusion changes from favourable to unfavourable (i.e. where the p-value increases to above 0.05; that is, where the imputed number of pulmonary exacerbations in the Colistimethate Sodium group has to increase by 100 δ % for statistical significance to be lost) will be presented, along with the smallest value of δ for which the p-value remains below 0.05.

For each of these 2 values of δ , the adjusted mean NCFB pulmonary exacerbation rates and 95% CIs in each treatment group, the adjusted rate ratio and 95% CI, and the p-value from the multiple imputation analysis using that value of δ will also be presented.

6.1.2. **CCI** Analyses with Additional Covariates and Interactions

In order to explore the statistical evidence for the degree of consistency of treatment effect at each level of a given prognostic factor, the negative binomial model used for the primary analysis will be repeated with the following additional effects included (one model per bullet point below):

- Country-by-treatment interaction;
- Number of NCFB pulmonary exacerbations requiring oral or intravenous antibiotics in the 12 months prior to study entry (# exacerbations) (1; 2; >2) and # exacerbations-by-treatment interaction;
- Previous usage of colistimethate sodium/colistin (Yes; No) and previous usage-by-treatment interaction;

This document is confidential.

- Age (as a continuous covariate) and age-by-treatment interaction;
- Age group (<65 years; >=65 years) and age group-by-treatment interaction;
- Gender (Female; Male) and gender-by-treatment interaction.

As was done for the primary analysis, the adjusted mean annual NCFB pulmonary exacerbation rates in each treatment group and the adjusted rate ratio with their 95% CIs will be estimated by the model. The number of subjects considered in the model will be provided by treatment group. P-values of the effects and interactions based on Wald chi-square test will also be presented.

6.1.3. [REDACTED] Analyses by Subgroup

The primary model was already fitted separately for each country, for each # exacerbations (1; 2; >2), and for each previous usage of colistimethate sodium/colistin (Yes; No) category, as planned in Sections 4.7.4, 4.7.4.5 and 4.7.4.6, respectively, of the Final SAP v2.0 dated 8th April 2021.

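### The deciding log-rank tests for time to first and first severe exacerbation ignore the macrolide factor used to stratify randomisation: valid, but slightly inefficient if that factor is prognostic

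*SAP*

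**What the plan says.** - **Time to first exacerbation (SAP 4.7.6.1).** "For the main analysis, a log-rank sum test will be used to compare the survival distributions of the two treatment groups". The endpoint's name is blacked out in that section. SAP 4.7.5 names time to first pulmonary exacerbation, and SAP 4.7.6.5 points back to 4.7.6.1, so the reading is secure enough.
- **Time to first severe exacerbation (SAP 4.7.6.5).** "The time to first severe NCFB pulmonary exacerbation will be analysed and tested using a log-rank test as detailed in Section 4.7.6.1", and then "A log-rank sum test will be used to compare the survival distributions of the two treatment groups".
- **Protocol 18.4.2.** "A log-rank sum test will be used to compare the treatment groups". No strata are named.
- **Code (SAP 4.14).** The PROC LIFETEST call has the single statement "STRATA treatment". Used alone, that statement defines the groups to be compared. It does not stratify the comparison.
- **Randomisation (SAP 3.7).** "Site and use of stable concomitant therapy with oral macrolides" "will be considered as factors for balancing randomisation, i.e. stratification factors".
- **Other analyses.** The negative binomial, Cox, repeated-measures, ANCOVA and non-parametric ANCOVA models all include macrolide use and country (SAP 4.9). The Cox model for time to first exacerbation is only supportive. None is named for the severe endpoint, for which the table list shows only Kaplan-Meier estimates.

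**The concern.** When randomisation is stratified by a factor that predicts outcome, treatment arms are more alike than simple randomisation would make them. A test that ignores the factor then overstates its own variance and tends to reject a little too rarely. The protocol's trial rationale treats macrolide use as something that could affect results, which is why it was balanced. SAP 4.9 gives no reason for leaving it out of the log-rank tests.

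These tests decide significance within a fixed sequence in which a test counts only if all earlier ones succeeded (SAP 4.7.5). The adjusted Cox model cannot replace a log-rank test that narrowly misses. Any avoidable loss of power therefore matters somewhat, even if it is small.

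**Working it through.** **1. Reproduce the plan's figure.** The SAP states no power for the log-rank tests, so the anchor is the blinded reassessment in SAP 3.9: annual rates 1.2701 (placebo) and 0.8256 (active), over-dispersion 0.273, and 145 per arm for 90% power. With the negative binomial Wald formula:

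n = (1.960 + 1.282)² × (1/1.2701 + 1/0.8256 + 2 × 0.273) / [ln(0.8256/1.2701)]² = 144.1 per arm, which rounds up to 145. The figure reproduces.

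**2. First events implied by the same inputs.** P(at least one event in a year) = 1 − (1 + k·rate)^(−1/k), with k = 0.273. This gives 66.4% on placebo and 52.5% on active. With 188 per arm and full follow-up: 188 × (0.664 + 0.525) ≈ 224 first events.

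**3. Main simulation.** 3000 trials per scenario.
- From the documents: about 377 subjects (376 simulated), two-sided 5% level, one year of follow-up, 20% dropout, placebo rate 1.2701, and total over-dispersion held near 0.273.
- Assumed, because the documents do not give them: 25% macrolide users; macrolide rate ratio 1.0 to 0.5; between-country SD of the log rate 0 to 0.4; 15 uneven countries with up to 7 sites each; blocks of 4 within site × macrolide.

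Power (%) for time to first exacerbation, by stratification of the log-rank test:

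| Treatment rate ratio | Macrolide rate ratio, country SD | None | Macrolide | Country × macrolide | Site × macrolide |
|---|---|---|---|---|---|
| 0.70 | 1.0, 0 | 64.1 | 63.9 | 59.4 | 45.7 |
| 0.70 | 0.7, 0.2 | 65.5 | 65.5 | 62.8 | 50.3 |
| 0.70 | 0.6, 0.3 | 64.6 | 66.3 | 64.9 | 51.7 |
| 0.70 | 0.5, 0.4 | 65.0 | 67.8 | 68.1 | 54.3 |
| 0.65 | 1.0, 0 | 79.1 | 78.8 | 75.6 | 61.7 |
| 0.65 | 0.7, 0.2 | 80.3 | 80.7 | 77.8 | 65.8 |
| 0.65 | 0.6, 0.3 | 80.3 | 81.2 | 79.5 | 65.5 |
| 0.65 | 0.5, 0.4 | 80.8 | 82.9 | 82.8 | 69.1 |

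The change from the unstratified test is -0.3 to +2.8 points for macrolide alone and -4.7 to +3.1 for ungrouped country × macrolide. For site × macrolide, the actual randomisation strata, it is about -11 to -18, because those strata are sparse. The Monte Carlo standard error of each power is at most 0.9 points.

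**4. Severe events.** With the severe rate assumed to be 25% of all exacerbations, macrolide stratification changed power by -0.2 to +0.7 points. Unstratified power was 30.4% to 33.0% at rate ratio 0.70 and 43.2% to 44.1% at 0.65.

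**5. Type I error.** The unstratified test gave 4.0% to 5.0% for any exacerbation and 4.5% to 5.3% for severe (standard error about 0.4 points).

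**6. Grouped country.** Two further sets of simulations used 377 subjects and 30% macrolide users.
- The first pooled countries with fewer than 20 subjects and ran 4000 trials per scenario. Macrolide alone changed power by -0.5 to +2.5 points. Macrolide × grouped country changed it by -2.0 to +2.2 points at country SD 0 to 0.2, -0.7 to +2.2 at SD 0.3, and +0.5 to +5.5 at SD 0.4 to 0.5. At SD 0.5 the unstratified type I error was 3.2% to 4.2%, against 4.4% to 5.1% stratified.
- The second held total over-dispersion near 0.273. Macrolide alone changed power by -0.1 to +3.0 points, and macrolide × grouped country by -1.7 to +5.4.

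**The case against.** The strongest reply is that nothing here is an error. The unstratified test controls type I error and follows the protocol. For time to first exacerbation, the SAP already plans a Cox model adjusted for country and macrolide use. Two other secondary tests, a t-test (SAP 4.7.6.7) and Fisher's exact test (SAP 4.7.6.8), also ignore both factors. All of this stands and limits the point to efficiency and consistency.

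Four stronger readings are tempting but unsupported.

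- **The tests simply lose power.** They do so only if the factors are prognostic, and the documents give no size for either effect. With no macrolide or country effect, stratifying by macrolide cost 0.2 to 0.3 points in the main simulation.
- **Country is known to be strongly prognostic.** SAP 4.7.4 makes by-country fits conditional on p<0.05 for country, and SAP Addendum 6.1.3 says "The primary model was already fitted separately for each country". That hints at a country effect, but no p-value or effect size is reported, and SAP 5.3.2 lists the by-country table without any condition. A simulation adding country effects to a dispersion of 0.273 did show 51.0% against 55.6% power at a country SD of 0.7. But log-normal country effects alone contribute over-dispersion of exp(SD²) − 1: 0.63 at SD 0.7 and 0.28 at SD 0.5. Both exceed the blinded 0.273, unless that estimate was already adjusted for country, which SAP 3.9 does not say. At SD 0.3 (0.09), that simulation showed no gain: 59.8% for both tests.
- **The analysis should reproduce the randomisation strata exactly.** With site × macrolide strata, power falls sharply.
- **A miss here would block every later secondary test.** The order of the sequence is blacked out in SAP 4.7.5, so what these tests would block cannot be read.

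**Conclusion.** The point holds as a modest improvement. Both deciding tests are unstratified, unlike the design and the regression models. They are valid, with type I error at or slightly below 5% within simulation error. If macrolide use or country is prognostic, they are somewhat conservative and less efficient.

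For time to first exacerbation, stratifying by macrolide use is worth about -0.5 to +3 points of power, so the possible cost is negligible. Little or no gain should be expected for severe events, where the reason for the change is consistency. These sizes rest on an assumed macrolide share of 25% to 30%, assumed macrolide and country effects, and an assumed share of severe events. The direction of the macrolide result was stable across the scenarios tried. The country result was not.

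**What to change.** - **Main test, both endpoints.** Use a log-rank test stratified by macrolide use: in PROC LIFETEST, `STRATA med / GROUP=treatment`. Amend SAP 4.7.6.1, 4.7.6.5 and 4.14 to match.
- **Supportive test.** Keep the unstratified log-rank test. The existing call is still needed for the Kaplan-Meier estimates and curves.
- **Optional further stratum.** Grouped country may be added if a grouping rule is fixed blind to treatment. It can gain about 5 points if country is strongly prognostic and lose about 2 if it is not. Do not use individual sites or ungrouped small countries. Addendum 6.1 and 6.1.3 already report inflated standard errors from small countries and three countries with no calculable rate ratio.
- **This trial.** Addendum 2.2 says the database is locked and the study unblinded, so the stratified results should be reported for both endpoints and labelled post hoc.

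The macrolide change costs one line of code and a short wording change. Grouped country costs more, because the rule must be written: the March 2022 note to file introduces a grouped-country variable after unblinding and does not state which countries were grouped.
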